6.1. Summary of Study Design

This is a 24-week, randomized, double-blind, placebo-controlled, Phase 2 study, comparing Rotigotine (Neupro, UCB pharma) with placebo for 24 weeks in approximately 100 patients with mild AD, defined as having a Visit 1 MMSE score of 18 to 26. Patients will be adaptively randomized (Lin et al. 2016) in a 1:1 ratio stratified by sex, age, APOE genotype, education and screening severity (MMSE) to one of the following treatment groups: Placebo group; RTG 4mg group. All patients started the treatment with a package containing 7 patches of RTG 2mg/placebo, and continued treatment with 6 packages, each one containing 30 patches of RTG 4mg/placebo depending on the arm of randomization. The primary hypothesis being tested is that Rotigotine will slow the cognitive and functional decline of AD as compared with placebo in patients with mild AD.

6.2. Timing of outcomes assessment

- 292 Preliminary screening
- Review of inclusion and exclusion criteria
- Informed consent obtained
- Demography
- Family and medical history
- Prior and concomitant medications
- Randomization and group assignment
- 299 Baseline evaluation (Day 1)
- Clinical assessment
- Neurophysiological assessment
- Post-treatment evaluation (Day 168-week 24)
- Clinical assessment
- Neurophysiological assessment

305 **6.3. Screening Phase**

306

307

308

309

310

311

312

313

314

315

316

317

At or before Visit 1, the study will be explained to the patient and caregiver. In the screening phase, all patients will undergo an extensive clinical investigation, including interviews on their medical history, a full neurological examination, the MMSE, a complete blood screening, neuropsychological assessment, neuropsychiatric evaluation, and magnetic resonance imaging. In the 30 days before entering the study, subjects will have to be clear of treatment with any drug inducing modulatory effects on the cerebral cortex excitability, such as antidepressants, benzodiazepines, anti-epileptic drugs, or neuroleptics. All AD patients will have to show a moderate level of dementia, as assessed by a neuropsychological evaluation including the MMSE (ranging from 18 to 26) and a standardized neuropsychological battery (Carlesimo et al,1996). All the patients will perform lumbar puncture for CSF biomarkers analysis for diagnostic purposes (Dubois et al., 2014). CSF t-tau and p-tau phosphorylated at Thr181 concentrations will be determined using a sandwich ELISA (InnotesthTAU-Ag, Innogenetics, Gent, Belgium) (Brem et al., 2013). Aβ1-42

levels will be determined using a sandwich ELISA (Innotest® β - amyloid (1–42), Innogenetics, Gent, Belgium), specifically constructed to measure A β containing both the first and 42nd amino acid, as previously described (Martorana et al., 2012). Patients will be excluded if they have either two or more hyperintense lesions with a diameter \geq 10mm or more than eight hyperintense lesions with a diameter between 5 and 9 mm on dual-echo MR images (Bozzali et al, 2011). Additionally, patients with TMS-related exclusion criteria will be not included in the study: presence of pacemakers, aneurysm clips, artificial heart valves, ear implants, or foreign metal objects in the eyes, skin or body, history of seizures (Rossi et al., 2009). All participants will sign a written informed consent after receiving an extensive disclosure of the experimental details.

6.4. Evaluation Phase

- During the week before starting RTG/PLC administration, and during the week at the end of 24-week
- treatment, AD patients will undergo clinical assessment and neurophysiological assessment in two different
- 330 days.

318

319

320

321

322

323

324

325

326

327

340

- 1) Clinical Assessment: before and after the 24 weeks of treatment the ADAS-Cog, ADCS-ADL,
- FAB and NPI will be administered.
- 2) Neurophysiological assessment: for EEG-TMS recordings, a TMS-compatible EEG equipment
- will be used for recording EEG activity from the scalp (BrainAmp 32MRplus, BrainProducts). The
- 335 EEG will be continuously acquired from 32 scalp sites positioned according to the 10-20
- International System. TMS-EEG recordings will be performed over the left prefrontal cortex (PFC)
- and left parietal cortex (I-PPC). To precisely position the coil over the cortical sites across different
- sessions, a neuronavigation system (Softaxic, E.M.S.) will be used. During the TMS-EEG session,
- each cortical site will be stimulated with 80 single TMS pulses (ISI: 0.3 Hz) (Koch et al., 2018).

6.5. Treatment Phase

- After recruitment and baseline assessments, AD patients will be assigned to RTG or PLC as add on
- to current AChEI therapy (donepezil or rivastigmine). We will use the Neupro® (Rotigotine
- 343 Transdermal System), a transdermal delivery system that provides rotigotine, a non-ergolinic DA

agonist, currently used for treatment of Parkinson's disease. When applied to intact skin, Neupro is designed to continuously deliver rotigotine over a 24-hour period. The precise mechanism of action of rotigotine, as a treatment for Parkinson's disease, is unknown although it is suggested to be related to its ability to stimulate D2 receptors within the brain. All of the non-ergoline agonists currently in clinical use are able to bind and activate the D2-like family of dopamine receptors, although they differ in their relative efficacy at these receptors. In preclinical studies, rotigotine has been already shown to act as a strong dopamine D2 receptor agonist (Van der Weide *et al.*, 1987; Tan, 2003). Moreover, in radioligand binding studies (Scheller *et al.*, 2009), rotigotine exhibited high affinity for the dopamine D3 receptor (Ki 0.71 nM), D2, D5 and D4 receptors (Ki 4–15 nM) and low affinity for the dopamine D1 receptor (Ki 83 nM). Furthermore, the continuous and uniform release of rotigotine from the transdermal delivery system has been demonstrated to give stable plasma drug levels over 24 h, providing a relatively continuous, more physiological, stimulation of dopamine receptors, with potential greater benefits on disease symptoms.

All treatments will be administered for 24 weeks with no interruptions. All treatments will be administered for 24 weeks with no interruptions. Rotigotine will be administered through a 4 mg transdermal patch (Neupro, UCB pharma), after having started with a 2 mg patch for 1 week. Transdermal patches of rotigotine have a release surface area of 10 or 20 cm² and contain 4.5 or 9 mg of rotigotine to release respectively 2 or 4 mg during a 24-hour period when applied to intact skin. The placebo transdermal patch contained in cardboard packaging will be identical to the rotigotine except for the absence of rotigotine.

SECTION 7: STUDY POPULATION

- Eligible patients will be males and females with mild to moderate AD, as specified in the entry
- 369 criteria that follow. Entered patients who meet all of the inclusion criteria and are not excluded by
- any of the exclusion criteria will be randomized and proceed to Evaluation Phase.

371 **7.1. Inclusion Criteria**

367

- Patients are eligible to be included in the study only if they meet all of the following criteria:
- 373 1. The patient (or if applicable the legally acceptable representative if different from the
- 374 responsible caregiver) and the responsible caregiver have signed the Informed Consent Form.
- The patient has probable AD, diagnosed according to National Institute of Neurological and
- 376 Communicative Disorders and Stroke and the Alzheimer's Disease and Related Disorders
- 377 Association (NINCDS-ADRDA) criteria.
- 378 3. The patient is a man or woman, aged $>50 \le 85$ years.
- 379 4. The patient has a Clinical Dementia Rating (CDR) total score of 0.5 or 1 (mild) and MMSE
- score of 18-26 (inclusive) at Screening.
- 381 5. Has at least one identified adult caregiver who is able to provide meaningful assessment of
- 382 changes in subject behavior and function over time and provide information on safety and
- tolerability, and is able to verify daily compliance with study drug
- 384 6. The patient has been treated with acetylcholinesterase inhibitor (AChEI), i.e., donepezil,
- galantamine, or rivastigmine, at the time of screening:
- for at least 6 months,
- the current dosage regimen and must have remained stable for ≥ 8 weeks,
- dosage regimen must have remained stable throughout participation in the study.
- The patients have performed lumbar puncture for CSF biomarkers analysis for diagnostic
- 390 purposes.

391 **7.2. Exclusion Criteria**

Patients will be excluded from study enrollment if they meet any of the following criteria:

- 393 1. Significant neurodegenerative disorder of the central nervous system other than Alzheimer's
- disease, e.g., Lewy body dementia, Parkinson's disease, multiple sclerosis, progressive supranuclear
- 395 palsy, hydrocephalus, Huntington's disease, any condition directly or indirectly caused by
- 396 Transmissible Spongiform Encephalopathy (TSE), Creutzfeldt-Jakob Disease (CJD), variant
- 397 Creutzfeldt-Jakob Disease (vCJD), or new variant Creutzfeldt-Jakob Disease (nvCJD)
- 398 2. The patient has history of seizure (with the exception of febrile seizures in childhood)
- 399 3. Diagnostic and Statistical Manual of Mental Disorders, Fourth Edition Text Revision
- 400 (DSM IV-TR) criteria met for any of the following within specified period:
- Major depressive disorder (current)
- Schizophrenia (lifetime)
- Other psychotic disorders, bipolar disorder, or substance (including alcohol) related
- disorders (within the past 5 years)
- 405 4. Metal implants in the head (except dental), pacemaker, cochlear implants, or any other non-
- 406 removable items that are contraindications to MR imaging.
- 407 5. Evidence of clinically significant disease including but not limited to pulmonary,
- 408 gastrointestinal, renal, hepatic, endocrine, cardiovascular or metabolic disorder (Patients with
- 409 controlled diabetes, or hypertension, or complete/partial right bundle branch block may be included
- 410 in the study).
- 411 6. Treatment currently or within 6 months before baseline with any of the following
- 412 medications:
 - Typical and atypical antipsychotics (i.e. Clozapine, Olanzapine)
- monoamine oxidase B inhibitors, anticholinergics etc)
- Carbamazepine, Primidone, Pregabalin, Gabapentin
- Memantine

420

7.3. Screening Procedures

- 421 Eligibility of participants in the study will be based on the results of sequential screening
- 422 procedures including medical history, physical examination, and neurological evaluation including
- 423 MRI or PET. The screening period allows patients adequate time to decide whether they wish to
- 424 participate in the study.

425

426

427

SECTION 8: TREATMENT

8.1. Treatments administrated

- 428 This study involves a comparison of Rotigotine treatment administered as transdermal patch for 24
- weeks compared with placebo. All patients started the treatment with a package containing 7
- patches of RTG 2mg/placebo, and continued treatment with 6 packages, each one containing 30
- patches of RTG 4mg/placebo depending on the arm of randomization.
- Subjects will be adaptively randomized (Lin et al. 2016) in a 1:1 ratio stratified by sex, age,
- APOE genotype, education and screening severity (MMSE) to one of the following treatment
- groups: Placebo group; RTG 4mg group.
- The investigational treatment packaging has a 1-part label. A unique randomization number
- 436 is printed on each label. Investigator staff identifies the investigational treatment package(s) to
- dispense to the patient. Labels include the following information: the name and address of the
- Sponsor, the study code, a unique identifier, appropriate contact information, and expiry date.
- Treatment is given to all patients for 24 weeks with no interruption.
- The investigational drug Neupro (rotigotine) is provided as transdermal patch contained in
- cardboard packaging. Placebo patches is identical in appearance and will be contained in identical
- 442 packages.
- At each post-Baseline visit during the treatment period, the number of patches dispensed to
- the patient/caregiver is recorded. Patient compliance with prescribed study drug is also assessed at

- each visit by questioning the patient and caregiver. Compliance data, including dates of any dose deviations and/or interruptions, and any other pertinent information are recorded in the source documentation.
 - Use of the following treatments are not allowed in combination with study treatment, due to confounding of efficacy and/or potential interaction with study treatment:
 - Any investigational drug: disallowed <60gg from screening
- General anesthetics are disallowed during the study except in case of emergency procedures requiring anesthesia. Episodic use of local anesthetics is allowed.
 - Antidepressant: stable treatment with no modification of dose with selective serotonin reuptake inhibitors (SSRIs), venlafaxine, moclobemide and mirtazapine for at least 6 months prior to the Screening Visit acceptable. Paroxetine and duloxetine should be used with caution. Dose modifications and initiation of treatment not allowed during the study.
 - Antiparkinsonian agents (e.g., levodopa, dopamine agonists, COMT inhibitors, amantadine, monoamine oxidase B inhibitors, anticholinergics etc.): disallowed for 6 months prior to screening and during the study.
 - Antipsychotics typical and atypical: disallowed for 3 months prior to screening and during the study.
 - Sedative/hypnotics: disallowed for 3 months prior to screening and during the study.

 Melatonin will be allowed anytime.
- The investigators or designees keep a record of all study drug received, and of all study drug dispensed to and returned by patients/caregivers.

8.2. Rationale for Selection of Doses

Neupro (Rotigotine Transdermal System) is indicated for the treatment of the signs and symptoms of idiopathic Parkinson's disease. The effectiveness of Neupro was demonstrated in randomized, controlled trials in patients with early-stage Parkinson's disease who were not receiving

concomitant levodopa therapy as well as in patients with advanced-stage Parkinson's disease on concomitant levodopa. We chose a low 4 mg dosage because such a drug has been previously found to be effective in modulating cholinergic activity and cortical plasticity in AD patients with no relevant side effects (Martorana et al, 2013; Koch et al., 2014). We chose to test the effects of RTG, which has an impact only on a subset of dopamine receptors, and not those of levo-dopa, which has a more global DA activation, because RTG can be administered with transdermal patches and it is well tolerated in AD patients (Martorana et al, 2013; Koch et al., 2014). PLC will be administered using a transdermal patch similar to those medicated. In all cases, each daily patch will be maintained for 24 h.

SECTION 9: EFFICACY AND SAFETY EVALUATIONS: OUTCOME

MEASURES

9.1. Primary Efficacy Measure

1) Global cognition [Time Frame: change from baseline to Week 24]: Alzheimer's Disease Assessment Scale - Cognitive Subscale (ADAS-Cog). The ADAS-Cog is the cognitive subscale of the ADAS (Rosen et al., 1984; Fioravanti et al., 1994) which consists of 11 tasks that measure memory, orientation, language, and praxis. The total score range is 0-70, with higher scores indicating greater impairment. ADAS-Cog scores have been shown to deteriorate by approximately 8-9 points per annum in patients with AD (Stern et al., 1994). The ADAS-Cog has a good inter-rater reliability and has been used widely as primary measure of cognitive change in contemporary studies of AD.

9.2. Secondary Efficacy Measures

1) Frontal cognitive functions [Time Frame: change from baseline to Week 24]: Frontal assessment battery (FAB). The Frontal Assessment Battery is a brief screening tool for the assessment of frontal lobe function (Appollonio et al., 2005). It is used to measure abstraction,

- fluency, impulsivity and primitive reflexes in patients who have a suspected frontal lobe deficit. A

 higher score indicates better performance. The FAB has been used to assess the effects of
- 498 rivastigmine on frontal functions in AD patients (Park et al., 2017)
- 499 2) Activities of daily living [Time Frame: change from baseline to Week 24]: Alzheimer's
- disease Cooperative Study Activities of Daily Living (ADCS-ADL). The ADCS-ADL includes 23
- 501 items that were derived from a larger set of items describing performance of activities of daily
- living (ADL) by Alzheimer's disease patients (Galasko et al., 1997). The ADCS contained 23 items
- 503 covering physical and mental functioning and independence in self-care. For each basic ADL
- (eating, walking, toileting, bathing, grooming, selecting, clothes), there is a forced choice of best
- response. All other ADL consist of a main question followed by subquestions (descriptors). The
- scores range from 0 to 78, with lower values indicating greater disability.
- Neuropsychiatric evaluation [Time Frame: change from baseline to Week 24]:
- Neuropsychiatric Inventory (NPI). The NPI assesses behavioral disturbances in dementia. The NPI
- is reliable and valid (Cummings, 1994) and has been reported to be sensitive to the effects of tacrine
- 510 (Kaufer et al., 1996). The NPI measures the following behavioral areas: delusions, hallucinations,
- agitation, depression, anxiety, euphoria, apathy, disinhibition, irritability, aberrant motor behavior,
- 512 night time behaviors, and eating disorders. Symptoms are rated in terms of frequency (0-4) and
- severity (0-3). Total score range is 0-144, where higher scores indicate higher behavioral
- 514 psychopathology.
- Neurophysiological markers of frontal lobe cortical activity [Time Frame: change from
- baseline to Week 24]: TMS-evoked cortical potentials assessed over the prefrontal cortex (PFC).
- 517 The combined use of transcranial magnetic stimulation (TMS) during electroencephalography
- 518 (EEG) allows to measure the cortical activity of the prefrontal cortex in AD patients (Kähkönen et
- al., 2005; Julkunen et al., 2008). We employ TMS-evoked cortical responses (i.e., TEPs) as a novel
- 520 probe of dopamine-agonist induced cortical excitability changes. As biomarkers we will measure
- 521 neurophysiological changes induced by dopamine-agonist over the left dorsolateral prefrontal

cortex (PFC), and over the left posterior parietal cortex (I-PPC), by evaluating the cortical excitability and oscillatory activity evoked by single-pulse TMS during EEG recordings. We chose to stimulate the left DLPFC since we want to assess the spatial specificity of our treatment, whereas the left PPC is chosen as a control site. Two sets of outcome measures will be obtained assessing cortical excitability (global mean field power-GMFP) and cortical oscillatory activity.

9.3. Safety Evaluations

Investigators are responsible for monitoring the safety of patients who have entered this study. The investigator is responsible for the appropriate medical care of patients during the study. The investigator remains responsible for following, through an appropriate health care option, AEs that are serious or that caused the patient to discontinue before completing the study. The patient should be followed until the event is resolved or explained. Frequency of follow-up evaluation is left to the discretion of the investigator.

9.4. Adverse Events and Other Safety Measures

A clinical study AE is any untoward medical event associated with the use of a drug or drug delivery system in humans. AE collection begins after the patient has signed informed consent and has received study drug. If a patient experiences a AE after signing informed consent, but before receiving study drug, the event will not be collected unless the investigator feels the event may have been caused by a protocol procedure.

At each clinic visit, AEs will be recorded, vital signs will be measured and physical and neurological examination will be performed. An independent Data Monitoring Committee will monitor the patients' safety according to the Data Monitoring Committee Charter.

SECTION 10. INFORMED CONSENT, ETHICAL REVIEW AND

REGULATORY CONSIDERATIONS

11.1. Informed Consent

The principal investigator is responsible for ensuring that the patient understands the potential risks and benefits of participating in the study, including answering any questions the patient may have throughout the study and sharing in a timely manner any new information that may be relevant to the patient's willingness to continue his or her participation in the trial.

The Informed Consent Form (ICF) will be used to explain the potential risks and benefits of study

participation to the patient/caregivers in simple terms before the patient is entered into the study,

553 and

552

554

555

556

557

558

559

569

570

571

572

to document that the patient is satisfied with his or her understanding of the risks and benefits of participating in the study and desires to participate in the study. The investigator is responsible for ensuring that informed consent is given by each patient or legal representative. This includes obtaining the appropriate signatures and dates on the ICF prior to the performance of any protocol procedures and prior to the administration of investigational product.

11.2. Ethical Review and Regulatory Considerations

- This study will be conducted in accordance with:
- 561 1) consensus ethics principles derived from international ethics guidelines, including the
- Declaration of Helsinki and Council for International Organizations of Medical Sciences (CIOMS)
- 563 International Ethical Guidelines
- 564 2) Institutional Review Board (IRB) Guidelines
- 565 3) Applicable laws and regulations.
- The investigator or designee will promptly submit the protocol to applicable ERB. An identification
- code assigned by the investigator to each patient will be used in lieu of the patient's name to protect
- the patient's identity when reporting AEs and/or other trial-related data.

11.3. Investigator Information

Physicians with expertise in neurology or geriatrics who have clearly documented extensive experience in AD trials will participate as investigators in this clinical study. In addition, licensed clinicians (neuropsychologists) who have clearly documented extensive experience in AD trials

may participate as investigators in this clinical study. Cognitive assessments must be administered by an individual trained in the use of these instruments. Neurophysiological recordings and analysis must be performed by experts in this field. All lumbar punctures must be performed by an appropriately trained individual.

2. STATISTICAL ANALYSIS PLAN

2.1. Determination of Sample Size

A total of 94 randomly assigned patients (47 per group) were planned on the basis of our previous study in which we assessed the effects of rotigotine on cortical plasticity and cognitive functions in a small sample of Alzheimer's disease patients (Koch et al., 2014). In that pilot study, a significant (although unpowered) difference was observed in pre-post (12 weeks) treatment with rotigotine in n=7 patients in both the cognitive measures MMSE (mean pre=21.73, SD=4.14; mean post=23.23, SD=3.93) and in FAB (mean pre=10.85, SD=4.43; mean post=12.32, SD=4.48). Treatment duration of the present study is twice larger than the one of the pilot study thus a larger effect size is expected. However, for precautionary reasons, we consider the same effect sizes found in the previous work (equal to 0.48 for MMSE and equal to 0.42 for FAB computed as post-pre means over standard deviation of difference post-pre), for the sample size calculation of the present study. In detail, adopting a two-tailed paired t-test, with type I error alpha=0.05 and a plausible correlation between pre-post measured variables of 0.7, the FAB effect size equal to 0.42 requires a minimum sample of n=46 for reaching a power of 0.8. For MMSE, this sample size allows to reach a power of 0.9. The minimum total sample size was then augmented up to N=92 considering the matched placebo group.

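### SAP 2.1: the pilot effect sizes behind the sample size appear to be imputed from an assumed correlation of 0.7, and do not fit a significant result in 7 patients

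*Combined protocol and SAP*

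**What the plan says.** Section 2.1 of the SAP (Determination of Sample Size) rests on one earlier study by the same group. It reports that "a significant (although unpowered) difference was observed in pre-post (12 weeks) treatment with rotigotine in n=7 patients", on two measures: "MMSE (mean pre=21.73, SD=4.14; mean post=23.23, SD=3.93") and "FAB (mean pre=10.85, SD=4.43; mean post=12.32, SD=4.48"). It gives no SD of change, observed correlation, test statistic or p-value for the pilot, and does not name the test used there.

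The plan then takes its inputs from that study: "we consider the same effect sizes found in the previous work (equal to 0.48 for MMSE and equal to 0.42 for FAB"), described as "computed as post-pre means over standard deviation of difference post-pre". The calculation is made by "adopting a two-tailed paired t-test, with type I error alpha=0.05 and a plausible correlation between pre-post measured variables of 0.7". The result is that "the FAB effect size equal to 0.42 requires a minimum sample of n=46 for reaching a power of 0.8". For MMSE the stated power at that size is 0.9. The 46 is doubled to 92 to allow for the placebo group.

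**The concern.** A paired t-test on a standardised change needs only the effect size and n. If 0.48 and 0.42 had been computed from observed within-patient changes, the calculation would have no use for a correlation. Yet 2.1 introduces "a plausible correlation between pre-post measured variables of 0.7", and calls it plausible, not observed. This suggests that the correlation was used to construct the SD of change, and that the effect sizes depend on it.

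The effect sizes also look too small for the significance reported: an effect of 0.4 to 0.5 SDs is not normally detectable in seven patients.

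These two numbers are the only quantitative basis in the plan for the size of the trial. If they depend on an assumed correlation, so do the stated n and power, and a reader of 2.1 cannot see that. If they conflict with the rest of the paragraph, at least one pilot figure is wrong.

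**Working it through.** **Inputs, all from section 2.1.** MMSE: 21.73 (SD 4.14) to 23.23 (SD 3.93), change 1.50. FAB: 10.85 (SD 4.43) to 12.32 (SD 4.48), change 1.47. Pilot n=7. Assumed correlation r=0.7. Two-sided alpha 0.05, paired t-test.

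**1. Effect sizes.** SD of change = √(s₁² + s₂² − 2·r·s₁·s₂); effect size dz = mean change / SD of change.

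- MMSE: √(17.140 + 15.445 − 1.4 × 4.14 × 3.93) = √9.806 = 3.131; dz = 1.50/3.131 = 0.479 (printed 0.48).
- FAB: √(19.625 + 20.070 − 1.4 × 4.43 × 4.48) = √11.910 = 3.451; dz = 1.47/3.451 = 0.426 (printed 0.42, a match if truncated).

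Nearby correlations do not recover the pair: r=0.6 gives 0.415 and 0.369, and r=0.8 gives 0.586 and 0.522.

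**2. Stated n and power (noncentral t, n−1 df).** FAB with dz=0.426 needs n=46 (power 0.807). With the printed 0.42 it needs n=47 (power 0.796 at 46). MMSE with dz=0.48 has power 0.890 at n=46. The plan's figures are reproduced, so its arithmetic is sound given its inputs.

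**3. Pilot significance at n=7.** t = dz·√7 on 6 df.

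- MMSE: 0.479 × 2.646 = 1.27, p=0.25.
- FAB: 0.426 × 2.646 = 1.13, p=0.30 (with the printed 0.42, t=1.11, p=0.31).

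The matching 95% intervals for mean change, using the critical value 2.447, are 1.50 ± 2.447 × 3.131/√7 = −1.4 to 4.4 (MMSE) and 1.47 ± 2.447 × 3.451/√7 = −1.7 to 4.7 (FAB).

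Two-sided p<0.05 at n=7 requires dz of at least 2.447/√7 = 0.925. That means an SD of change of at most 1.62 (MMSE) or 1.59 (FAB), hence r of at least 0.92 or 0.94. A one-sided test would still need dz of at least 0.734. Conversely, 0.48 and 0.42 first reach two-sided p<0.05 at n=20 and n=25.

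**4. Is n=7 consistent with the printed means?** Seven whole-number scores give means in steps of 1/7.

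- 21.73 × 7 = 152.11, but 152/7 = 21.71.
- 23.23 × 7 = 162.61, but 162/7 = 23.14 and 163/7 = 23.29.
- 12.32 × 7 = 86.24, but 86/7 = 12.29.
- 10.85 is reachable only by truncating 76/7 = 10.857.

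So either the scores were adjusted, which the documents do not say, or the means are not from seven patients.

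**5. Sensitivity to the correlation** (paired t-test, the plan's means and SDs; values other than 0.7 are assumptions shown for range):

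| r | FAB dz | FAB n for 80% power | FAB power at n=46 | MMSE power at n=46 |
|---|---|---|---|---|
| 0.5 | 0.330 | 75 | 0.59 | 0.69 |
| 0.6 | 0.369 | 60 | 0.69 | 0.79 |
| 0.7 | 0.426 | 46 | 0.81 | 0.89 |
| 0.8 | 0.522 | 31 | 0.93 | 0.97 |

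If the pilot really was significant at n=7 by a paired t-test, dz was at least 0.925 and the same calculation would need at most 12 patients.

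**The case against.** The strongest reply is that an SD which is not printed may still have been measured. The FAB match is also imperfect: 0.426 rounds to 0.43, and exactly 0.42 corresponds to r of about 0.691. This stands as a limit. Imputation is an inference, though a strong one, because a single assumed r recovers both values and has no other use in the calculation. A reader might conclude that the SD of change was never measured in the pilot; the documents do not establish that.

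Second, the paired t-test is named for sizing this trial, not for the pilot. A signed-rank test with all seven changes positive could be significant with dz as low as 1/√7 = 0.378. That is possible but needs one patient to carry most of the total change. It would remove the conflict in step 3, but not the question of where the SD came from.

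Third, it is tempting to say that either the SD used is about twice the true one or the pilot was not significant. The documents do not force that choice. Step 4 gives a reason to doubt the pilot n itself, and with 20 or more (MMSE) or 25 or more (FAB) patients the printed effect sizes would be significant.

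Fourth, the plan's description of its choice as precautionary is fair in context: it refers to keeping the 12-week effect rather than assuming a larger one at 24 weeks, and makes no claim about the SD.

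Finally, the calculation concerns a within-arm change on FAB and MMSE, whereas the primary analysis compares arms on ADAS-Cog. That is a separate matter. It limits the practical weight of this point but does not resolve it.

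**Conclusion.** The point holds as one of provenance and internal consistency; there is no arithmetic slip. The effect sizes are presented as pilot results but appear to be derived from an assumed correlation of 0.7. Under a two-tailed paired t-test, a pilot of seven patients, a significant change on both measures, and effect sizes of 0.48 and 0.42 cannot all be right. Which of the three is wrong cannot be settled from the documents.

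A reader might infer that the trial is underpowered. The documents do not support that either, because the direction is unknown. Lower correlations take FAB power at n=46 down to 0.59 at r=0.5. A pilot that was significant as stated would imply a larger effect and power above 0.99. These ranges take the printed means and SDs as correct.

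**What to change.** In section 2.1, check the pilot n and the test behind its significance statement. Take the SD of the within-patient changes directly from the sponsor's own pilot data, and restate the effect sizes, required n and power from it.

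If that SD cannot be retrieved:

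- say that the effect sizes assume a correlation of 0.7, in place of the statement that they were found in the earlier study;
- correct or remove the claim of significance unless the pilot test supports it;
- print power at the planned size for correlations from 0.5 to 0.8.

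The word precautionary can stay where it refers to the longer treatment period. The cost is SAP wording and a short recalculation, with no change to enrolment. The downside is that the stated power may become a range or less favourable.
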